5.3.5.2 Clinical Protocol

1. RECIST 1.1-defined disease progression. In cases where RECIST cannot be applied, progression should be based on unequivocal evidence of progressive disease sufficient to require a change in therapy. In the angiosarcoma cohort 1, disease progression for withdrawal refers to disease progression while receiving TRC105 plus pazopanib combination therapy.
2. A need for surgery, radiation, or for other anticancer therapy not specified in the protocol.
3. Unable to tolerate pazopanib during cycle 1 (phase 1b, dose levels -1, 1, 2 and expanded cohort 1 only).
4. Lost to follow-up or noncompliant.
5. Any TRC105 dose delay > 2 days between cycle 2 day 1 and cycle 2 day 28 (phase 1b only).
6. Pregnancy. Pregnant patients should be followed for the duration of the pregnancy and the outcome of the pregnancy should be documented.
7. Arterial thrombosis of any grade (including cerebrovascular ischemia, cardiac ischemia/infarction, or peripheral or visceral arterial ischemia) or grade 3 or 4 venous thrombosis (including pulmonary embolism).
8. Missed study drug treatment for > 8 consecutive weeks (i.e., both TRC105 and pazopanib dosing held). However, patients who cannot tolerate pazopanib or TRC105 therapy and who demonstrate a response of complete response (CR), partial response (PR) or stable disease (SD) with the combination and are thought to benefit from continued single agent therapy may continue on study on TRC105 or pazopanib alone.

5.3.5.2 Clinical Protocol

6. TREATMENT OF PATIENTS

6.1. Description of TRC105 Study Drug

TRC105 is a genetically engineered human/murine chimeric monoclonal antibody directed against human CD105 found on the surface of proliferating endothelial cells.

6.1.1. Composition of TRC105

TRC105 is an IgG1, kappa immunoglobulin containing murine light- and heavy-chain variable region sequences and human constant region sequences. TRC105 has an approximate molecular weight of 148 kDa.

6.1.2. TRC105 Dose Level

6.1.2.1. Phase 1b

Each patient will be dosed with 6 (Dose Level -1), 8 (Dose Level 1) or 10 mg/kg (Dose Level 2), or 15 mg/kg (Dose Level 3) The maximum weight that should be used for purpose of dose calculation is 85 kg for women and 100 kg for men. Thus, the maximum dose that should be given to a woman at the 10 mg/kg dose is 850 mg and at the 15 mg/kg dose is 1275 mg, and the maximum dose that should be given to a man at the 10 mg/kg dose is 1000 mg and at the 15 mg/kg dose is 1,500 mg. TRC105 is distributed according to lean body mass rather than overall body weight. Patients who are overweight would be at risk for high serum levels of TRC105 if the doses were not capped. Eighty-five kg for women and 100 kg for men represent accepted maximum lean body masses for the two genders.

For dose levels -1, 1, 2, and expanded cohort 1 the first weekly TRC105 dose will be given on cycle 2 day 1 following two, three, or four weeks of treatment with pazopanib alone. The first weekly dose will be split into two doses whereby 3 mg/kg will be administered on cycle 2 day 1 and the balance will be administered on cycle 2 day 4). The entire weekly dose of TRC105 (6, 8 or 10 mg/kg) is then given on cycle 2 day 8 and weekly thereafter in combination with oral pazopanib.

For dose levels 3 and expanded cohort 2, TRC105 dosing will begin on cycle 1 day 1 with the first weekly dose split into two doses whereby 3 mg/kg is administered on cycle 1 day 1 and 7 mg/kg is administered on cycle 1 day 4. The entire weekly dose of TRC105 at 10 mg/kg is then given on cycle 1 day 8 and weekly until cycle 2 day 1 when TRC105 is administered at 15 mg/kg every two weeks. The DLT evaluation period, for purposes of dose escalation, will be cycle 2. Each cycle will be 28 days in duration.

6.1.2.2. Phase 2

Each patient, including patients in the angiosarcoma cohort, will be dosed with 10 mg/kg up to a **maximum dose of 850 mg of TRC105 for women and 1,000 mg of TRC105 for men (i.e., 85 kg for women and 100 kg for men is the maximum weight that should be used for purposes of dose calculation on this study).** TRC105 is distributed according to lean body mass rather than overall body weight. Patients who are overweight would be at risk for high serum levels of TRC105 if the doses were not capped. 85 kg for women and 100 kg for men represent accepted

5.3.5.2 Clinical Protocol

maximum lean body masses for the two genders. The first weekly TRC105 dose will be given on cycle 1 day 1. The first weekly dose will be split into two doses whereby 3 mg/kg will be administered on cycle 1 day 1 and the balance will be administered on cycle 1 day 4. The entire weekly dose of TRC105 (10 mg/kg) is then given on cycle 1 day 8 and weekly thereafter. Each cycle following will be 28 days in duration.

TRC105 may be administered every two weeks starting with cycle 2 day 1, once it is determined that the every two week dosing MTD has not been exceeded. SPONSOR WILL SEND NOTIFICATION TO PROCEED WITH EVERY TWO WEEK DOSING.

- TRC105 will be administered at 10 mg/kg weekly during cycle 1.
 - The first weekly TRC105 dose (10 mg/kg) will be split into two doses whereby 3 mg/kg is administered on cycle 1 day 1 and the balance is administered on cycle 1 day 4.
- Starting on cycle 2 day 1 and beyond, TRC105 may be administered every two weeks on days 1 and 15 at 15 mg/kg.

6.1.3. TRC105 Packaging and Labeling

TRC105 may be provided in one or more of the following presentations.

Phosphate Buffered Saline Formulation (7 mg TRC105/mL)

210 mg TRC105/30 mL single-use vial

20 mM L-Histidine/L-Histidine Monohydrochloride, 240 mM Trehalose, 0.01% Polysorbate 20 Formulation (25 mg TRC105/mL)

100 mg TRC105/4 mL single-use vial

200 mg TRC105/8 mL single-use vial

400 mg TRC105/16 mL single-use vial

6.1.4. TRC105 Storage and Shipping

TRC105 must be stored upright between 2 °C and 8 °C (36 °F to 46 °F) and protected from light.

6.1.5. TRC105 Preparation

TRC105 will be prepared in the pharmacy and diluted into normal saline using appropriate aseptic technique. TRC105 will be administered using an in-line 0.2 micron filter. No incompatibilities between TRC105 and polyvinyl chloride or polyolefin bags have been observed. Multiple vials will be required for a single dose. The following formulae should be used to calculate the volume of TRC105 to be added to normal saline:

- Patient weight (kg) × dose level (mg/kg) divided by TRC105 concentration (mg/mL) = volume of TRC105 (mL) to be administered.

The volume of TRC105 that is to be administered can be rounded up or down to the nearest 1.0 mL; in the case of an increment of 0.5 mL the volume should be rounded up. **The maximum**

5.3.5.2 Clinical Protocol

weight that should be used for dose calculation in this study is 85 kg for women and 100 kg for men (note: there is not a weight restriction for enrollment purposes). If the patient's weight changes by > 10% during the study, the dose of TRC105 will be recalculated. At that time a new baseline weight will be established such that subsequent weight changes by >10% from the new baseline weight would require further recalculation of the TRC105 dose. The calculated volume of TRC105 will be diluted with normal saline. Appropriate judgment should be exercised in withdrawing an adequate amount of saline necessary to permit injection of the appropriate volume of antibody into a normal saline bag in accordance with the dose needed. The final TRC105 concentration must be between 0.6 mg/mL and 10 mg/mL. The prepared TRC105 must be gently inverted several times in order to ensure a homogeneous solution. The diluted infusion solution of TRC105 should be used within 8 hours of preparation if stored at room temperature, or within 24 hours of dilution if stored at 2° to 8°C (36° to 46°F). The expiration time should be labeled on the bag. If the diluted infusion solution of TRC105 cannot be infused within 8 hours of preparation (i.e.: the prepared infusion is at room temperature for more than 8 hours), a second bag will be prepared that contains the balance of the planned dose that was not already delivered. The prepared solution should not be frozen.

6.1.6. TRC105 Administration

Patients should be encouraged to drink abundant fluid (e.g., two eight ounce glasses of water or juice) prior to the first treatment. Intravenous hydration prior to and during therapy is left to the discretion of the Investigator, but should be considered for patients that may be volume depleted.

The following TRC105 premedications should be administered 2 hours to 30 minutes prior to the start of each infusion:

- Acetaminophen 650 mg p.o. x 1
- Methylprednisolone 100 mg i.v. will be given prior to the cycle 1 day 1 and cycle 1 day 4 infusions. In addition, methylprednisolone will be given in the case of a delay of ≥ 10 days between any two scheduled weekly doses or in the case of a delay of ≥ 17 days between any two scheduled every other week doses, or if the patient develops an infusion reaction \geq grade 2 during the immediate prior infusion.
- Famotidine 20 mg i.v. or p.o. (or similar H2 blocker) x 1. Famotidine (or similar H2 blocker) may be discontinued starting with Cycle 2 for weekly dosing, Cycle 3 for every two week dosing, in the absence of infusion reactions with the prior dose.
- Cetirizine 10 mg i.v. or p.o. x 1 (or similar oral or intravenous antihistamine). Cetirizine (or similar oral or intravenous antihistamine) may be discontinued starting with Cycle 2 for weekly dosing, Cycle 3 for every two week dosing, in the absence of infusion reactions with the prior dose.

TRC105 infusions will begin 2 hours to 30 minutes following the completion of the TRC105 premedication, including the methylprednisolone infusion.

TRC105 will be administered intravenously utilizing an infusion pump. TRC105 has been demonstrated to be compatible with polyethylene lined, non-DEHP infusion sets and polyvinyl chloride, non-DEHP infusion sets. TRC105 is required to be administered with a 0.2 micron downstream filter. The attachment of the infusion pump administration set to the i.v. bag and

5.3.5.2 Clinical Protocol

transport of the TRC105 study drug to the patient will be performed as per standard study site procedures.

Following the appropriate premedication regimen, the first weekly TRC105 dose will be split into two doses whereby 3 mg/kg is administered (on cycle 2 day 1 for the phase 1b portion dose levels -1, 1, 2, and expansion cohort 1 and cycle 1 day 1 for the phase 1b dose levels 3, expansion cohort 2 and phase 2 portion) over 4 hours (+/- 15 minutes) and the balance (e.g., 5 mg/kg for Dose Level 1) is administered on day 4 over 2 hours (+/- 15 minutes). Do not increase the infusion rate above 25 mg/min. Thereafter, the full (e.g., 8 mg/kg for Dose Level 1) TRC105 dose will be administered i.v. weekly over 1 hour (+/- 15 minutes) (e.g., the first full dose is given on cycle 2 day 8 for the phase 1b portion and cycle 1 day 8 for the phase 2 portion).

Every two week infusions will begin on cycle 2 day 1 for phase 1b dose levels 3 and expanded cohort 2. Patients must complete at least one 4 hour infusion without the development of any infusion reactions, in order to reduce the subsequent TRC105 infusion to 2 hours (+/- 15 minutes) and complete a 2 hour infusion without the development of any infusion reactions in order to reduce subsequent TRC105 infusions to 1 hour (+/- 15 minutes). See [Table 8](#) [Table 9](#) for ideal dosing schemas. Patients with infusion reactions of any kind should be managed appropriately (see Section [6.1.8](#)) and are not permitted to reduce the duration of the next planned infusion.

The rate of TRC105 infusion must not exceed 25 mg/min. When the i.v. bag containing TRC105 is empty, flush the i.v. line with a 20 mL normal saline. The dose level, time of transfer to i.v. bag, and the infusion start and stop times must be recorded in the source documents.

Table 8: TRC105 10 mg/kg Weekly Ideal Dosing Schema

	C1D1	C1D4	C1D8	C1D15	C1D22	C2D1+
TRC105 Dose (mg/kg)	3	7	10	10	10	10
Infusion Duration (hours)	4	2	1	1	1	1
Premedication						
Methylprednisolone (mg)	100	100	0	0	0	0
Famotidine (mg)	20	20	20	20	20	0
Cetirizine (mg)	10	10	10	10	10	0
Acetaminophen (mg)	650	650	650	650	650	650

5.3.5.2 Clinical Protocol

Table 9: TRC105 15 mg/kg Every Two Weeks Ideal Dosing Schema (Ph1b Dose Level 3)

	C1D1	C1D4	C1D8	C1D15	C1D22	C2D1	C2D15	C3D1+
TRC105 Dose (mg/kg)	3	7	10	10	10	15	15	15
Infusion Duration (hours)	4	2	1	1	1	1	1	1
Premedication								
Methylprednisolone (mg)	100	100	0	0	0	0	0	0
Famotidine (mg)	20	20	20	20	20	20	20	0
Cetirizine (mg)	10	10	10	10	10	10	10	0
Acetaminophen (mg)	650	650	650	650	650	650	650	650

6.1.7. TRC105 Dose Modification/Dose Delays

In cycle 3 and beyond (and beginning in cycle 2 of the phase 2 portion), TRC105 dose reductions are allowed for grade 3 or 4 related adverse events that resolve to grade 1 or baseline (including anemia). Treatment dose delays cannot exceed 8 consecutive weeks (i.e., both TRC105 and pazopanib dosing held). However, patients who cannot tolerate pazopanib or TRC105 therapy and who demonstrate a response of complete response (CR), partial response (PR) or stable disease (SD) with the combination and are thought to benefit from continued single agent therapy may continue on study on TRC105 or pazopanib alone per Section 5.3 of the protocol.

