5.3.5.2 Clinical Protocol

Table 3: Dose Limiting Toxicity Definition and Criteria

Toxicity Category	Drug-Related Toxicity/Grade
Hematologic	Grade 4 neutropenia for ≥ 5 days
	Febrile neutropenia: grade 4 neutropenia with fever > 38.5 °C both sustained over a 24 hour period.
	Neutropenic infection: grade ≥ 3 neutropenia with grade ≥ 3 infection
	Anemia \geq grade 4
	Grade > 4 thrombocytopenia or grade ≥ 3 thrombocytopenia and grade ≥ 3 hemorrhage
Nonhematologic	Grade 3 or 4 nonhematologic toxicity with the following exceptions: 
 • Nausea, vomiting or diarrhea for < 48 hours^a • Asymptomatic electrolyte abnormalities that are corrected to grade 1 or better in < 72 hours^b • headache lasting less than 48 hours

^aPatients with related grade 3 or 4 diarrhea, nausea or vomiting for ≥ 48 hours despite optimal medical therapy will require a one-level dose-reduction of TRC105.

^bPatients with related grade 3 or 4 electrolyte abnormalities that persist for ≥ 72 hours will require a one level dose-reduction of TRC105.

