5.3.5.2 Clinical Protocol

Table 10: Allowable TRC105 Dose Modifications

Toxicity Attributed to TRC105	Dose Adjustment for Next Dose of TRC105	
	10 mg/kg weekly	15 mg/kg every 2 weeks
Grade 1 or 2	Maintain Dose Level	Maintain Dose Level
Grade 3 or 4		
• 1 st appearance	8 mg/kg weekly	12 mg/kg every 2 weeks
• 2 nd appearance	6 mg/kg weekly	10 mg/kg every 2 weeks
• 3 rd appearance	4 mg/kg weekly	8 mg/kg every 2 weeks
• 4 th appearance	Discontinue TRC105 treatment permanently	Discontinue TRC105 treatment permanently*
*After discussion with and agreement of the Sponsor, patients receiving TRC105 every two weeks have the option to return to weekly dosing at the lowest level (i.e., 4 mg/kg weekly), if 8 mg/kg every 2 weeks is not tolerable (i.e., 4 th appearance of a Grade 3 or 4 toxicity attributable to TRC105 occurs) and the investigator believes that the patient is receiving benefit from the treatment.		

Patients with arterial thrombosis or grade 3 or 4 venous thrombosis should be removed from study. Patients with grade 1 or 2 venous thrombosis who require anticoagulation will have their TRC105 therapy interrupted. TRC105 therapy may resume once the following criteria are met:

- The patient is on a stable dose of heparin or low molecular weight heparin.
- The patient has a platelet count > 100,000.
- The patient has not had a hemorrhagic event of grade 2 or higher while on study.
- The patient does not have a pathological condition that carries a high risk of bleeding (e.g., tumor involving major vessels).
- The patient is benefiting from TRC105 therapy (no evidence of disease progression).

TRC105 and pazopanib should be held for two weeks prior and for two weeks following surgical procedures. However, resumption of study treatment can be shorter (but no less than 7 days) or longer than two weeks based on clinical judgement of adequate wound healing and recovery from the procedure. For **minor procedures** (e.g., port placement), TRC105 (and pazopanib) should be held for at least 1 week prior and for at least 1 week after (or until adequate healing).

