5.3.5.2 Clinical Protocol

- The study population for efficacy will include all safety population patients who have baseline and follow-up tumor measurements as required for assessment by RECIST 1.1.

Patients who experience DLT who receive less than the prescribed dose of TRC105 or pazopanib due to documented toxicity in cycle 2 will be considered evaluable for dose escalation purposes.

Only those patients who are deemed "ineligible" or who receive no therapy (i.e. no TRC105 or pazopanib) will be eliminated from the analysis. Ineligible patients who receive therapy will not be included in the assessment of efficacy endpoints, but their data will be included in the assessment of all adverse event reporting.

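### Phase 1b: the Table 3 footnotes require a TRC105 reduction for prolonged gastrointestinal or electrolyte toxicity, but section 6.1.7 opens reductions only from cycle 3, so a remaining cycle 2 infusion has conflicting instructions

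*Combined protocol and SAP*

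**What the plan says.** Five places in the combined protocol and SAP bear on this.

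- **Table 3, footnotes a and b (section 4.1.1.1, repeated in the synopsis).** For gastrointestinal toxicity: "diarrhea, nausea or vomiting for ≥ 48 hours despite optimal medical therapy will require a one-level dose-reduction of TRC105". For electrolytes: "electrolyte abnormalities that persist for ≥ 72 hours will require a one level dose-reduction of TRC105". Neither footnote names a cycle or a start time.
- **Section 6.1.7.** "In cycle 3 and beyond (and beginning in cycle 2 of the phase 2 portion), TRC105 dose reductions are allowed", and this is "for grade 3 or 4 related adverse events that resolve to grade 1 or baseline (including anemia").
- **Table 10.** It sits under section 6.1.7, and its column heading is "Dose Adjustment for Next Dose of TRC105".
- **Section 5.3, criterion 5 (also in the synopsis).** A patient is withdrawn from treatment for "Any TRC105 dose delay > 2 days between cycle 2 day 1 and cycle 2 day 28 (phase 1b only").
- **Section 10.1.1.1 (similar wording in 4.1.1.1).** For escalation decisions, the rule on patients with a DLT reads: "receive less than the prescribed dose of TRC105 or pazopanib due to documented toxicity in cycle 2 will be considered evaluable".

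Sections 4.1.1.1 and 6.1.2.1 place the phase 1b DLT window in cycle 2.

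**The concern.** The toxicities in footnotes a and b are the ones that outlast the exceptions in Table 3. When they occur in cycle 2 they are DLTs. The protocol makes a TRC105 reduction mandatory for them, yet the section governing reductions does not open in phase 1b until that cycle is over. It also adds a condition, recovery to grade 1 or baseline, that the footnotes lack.

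A DLT is not itself a listed reason for withdrawal in section 5.3, so the patient may still be on treatment when the next infusion falls due. One site could give the full dose, another a reduced dose, and a third could hold the infusion and so trigger withdrawal. Each could point to a passage in support. At stake is consistent and safe handling of a patient who has just had a serious toxicity.

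**Working it through.** No sample size, power or error rate is involved. The check compares the passages and counts infusion days.

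**1. Which events carry the mandate.** Table 3 attaches a required reduction only to the two groups in footnotes a and b. It attaches none to the hematologic DLTs or to other grade 3 or 4 nonhematologic toxicity.

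**2. Whether 6.1.7 sets a start date.** It gives cycle 3 for phase 1b and cycle 2 for phase 2. The synopsis repeats cycle 2 as the start for the phase 2 soft tissue sarcoma patients and angiosarcoma cohort 1. Without a start-date meaning, the distinction between the phases would do nothing. The limit is implied, because 6.1.7 contains no express ban before cycle 3.

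**3. When the conflict reaches an infusion.** The infusion days come from section 4.1.2.2 and Tables 4 and 5. The threshold (48 h = 2 days, 72 h = 3 days) must be met before the last cycle 2 infusion.

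| Schedule | Cycle 2 infusion days | Last | Latest gastrointestinal onset | Latest electrolyte onset |
|---|---|---|---|---|
| Dose level 3, Expanded Cohort 2 | 1, 15 | 15 | about day 15 − 2 = 13 | about day 15 − 3 = 12 |
| Levels −1, 1, 2, Expanded Cohort 1 | 1, 4, 8, 15, 22 | 22 | about day 22 − 2 = 20 | about day 22 − 3 = 19 |

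If the threshold is met later, the next infusion is cycle 3 day 1. Section 6.1.7 allows a reduction by then, so the timing conflict does not arise.

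**4. The courses open at that infusion**, taking day 15 at dose level 3:

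- *Reduced dose.* This fits Table 3 and the heading of Table 10. It falls before the start in 6.1.7, and the event may not yet meet the recovery condition.
- *Full dose.* This fits the timing in 6.1.7. It fits Table 3 only if the required reduction may wait until cycle 3, which no passage says.
- *Hold until cycle 3 day 1.* The delay is 28 + 1 − 15 = 14 days (28 + 1 − 22 = 7 days for the last weekly infusion). Both exceed 2 days, so criterion 5 applies and treatment ends. A delay within 2 days only moves the same question to day 17 at the latest.
- *Withdraw on the investigator's judgment.* Section 5.3 provides for this.

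So a course that reduces at the next dose and keeps the patient on treatment departs from 6.1.7. A course that follows 6.1.7 and continues treatment needs a deferral that the protocol does not state.

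**5. Reach.** Section 2.2.1.4 reports 18 patients treated at the weekly levels without a DLT. Section 10.1.1 plans up to 30 in phase 1b, which leaves at most 30 − 18 = 12, and at least 6 are to be treated at the every-two-week MTD or top level.

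**The case against.** The best reply is that the texts can be read together. Table 3 gives no timing and 6.1.7 is permissive, so either the specific DLT footnote governs these events and 6.1.7 governs other reductions, or the required reduction starts when 6.1.7 opens. Table 10 sits under 6.1.7 and may share its limit. The evaluability wording in 10.1.1.1 could describe a missed infusion or a pazopanib reduction, so it does not prove that reduced TRC105 doses are expected in cycle 2. All of this is fair, and both readings are possible. But they give opposite instructions for the same infusion, and the protocol does not choose between them. The objection explains how a site might resolve the conflict without removing it.

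Other limits on the point stand in full:

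- A reader might infer that every phase 1b DLT is affected. Table 3 mandates a reduction for the two prolonged toxicity groups only.
- A reader might infer that no compliant course exists. Withdrawal is one.
- A reader might infer that a one-level step is undefined at 15 mg/kg every two weeks. Table 10 has a column for that schedule with a stated first step, and dose level 2 is on a different, weekly schedule.
- A reader might take any event in the first half of cycle 2, or the whole of the first two cycles at dose level 3, as the size of the problem. The duration thresholds shorten the first, and cycle 1 lies outside the DLT window there.

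**Conclusion.** The inconsistency is real and narrow. It concerns phase 1b patients with prolonged, related grade 3 or 4 gastrointestinal or electrolyte toxicity whose duration threshold is met while a cycle 2 infusion remains. With no DLT reported at the weekly levels, it bears mainly on dose level 3 and Expanded Cohort 2: at most about 12 further patients if phase 1b stays within its ceiling, and only those with a qualifying early event. The documents give no rate for such events, so the expected number cannot be stated.

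A reader might also infer that differing practice would distort the MTD. The documents do not support that. The MTD depends on the proportion of patients with a DLT (sections 4.1.1.1 and 10.1.1). These patients have already had one, and those given less than the prescribed dose because of documented toxicity stay evaluable. What happens at the next infusion cannot undo a counted event.

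The conclusion assumes that the cycle 3 wording in 6.1.7 is a start date and that the footnotes apply to events in the DLT window. It takes no view on which rule is clinically right. Because the wording governs re-dosing after a serious toxicity, it should be corrected.

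**What to change.** Reconcile Table 3 footnotes a and b, their copy in the synopsis, section 6.1.7, Table 10 and withdrawal criterion 5 in section 5.3 (with its synopsis copy) into one instruction for these toxicities before cycle 3 in phase 1b. The instruction should state:

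- when the required reduction takes effect;
- whether the recovery condition in 6.1.7 applies to it;
- how it interacts with the 2-day delay rule.

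Align the evaluability wording in sections 4.1.1.1 and 10.1.1.1 with the result. Which rule applies is for the sponsor's clinicians. The cost is protocol wording only: no added patients, data or analyses.
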